transmission, casual contact misconceptions, general information and course of illness. It increased significantly with STAR compared to the control condition that provided similar HIV knowledge, presumably due to the decrease in cognitive errors from the STAR training. **Self-Efficacy for Condom Use Scale.** The scale contains 13 items that reflect the context of condom use, such as “could use a condom when I’m very upset” and was found to have a good factor structure and a strong alpha of 0.9.(87) Self-efficacy in emotionally stressful situations improved in STAR, presumably due to the improvement in affect management. **Affect Dysregulation Scale.** A six item scale assessing adolescents’ perceived abilities to manage emotional upset (e.g., “In the past three months, I have had trouble controlling my feelings.” The scale has a Cronbach’s alpha = .72. The scale correlates strongly with behavioral risk in a sample of youth in mental health treatment.(48) **Advantages of Condom Use Scale.** (88) This scale has 13 items (alpha=.78) to assess cognitions of condom use (e.g. “it would be safer”), which are relevant to the interventions focus on cognitive monitoring. Because of the prevalence of psychological symptoms and trauma history, this will be assessed to describe the sample. **Childhood Trauma Questionnaire (CTQ).** This is a 28-item youth self-report measure that assesses history of physical, sexual and emotional maltreatment. It yields a subscale score for each domain of maltreatment as well as a total score. The CTQ has demonstrated excellent psychometric properties in clinical and non-clinical samples ($\alpha = .92$).(89) **The Brief Symptom Inventory (BSI).** This measure yields symptom scales and global indices and has norms for adolescents. The reliability, validity, and utility of the BSI instrument have been tested in more than 400 research studies.(90)

Participants will also complete the SEF and CSQ-8 in paper and pencil format (see above) following the end of each session to assess the acceptability and relevance of the session.

Phase 2 Pilot and RCT Measures

HIV related Risk Behaviors. The Adolescent Risk Behavior Assessment (ARBA) is a computer-assisted structured interview designed specifically for use with adolescents to assess their self-reported sexual and drug behaviors associated with HIV infection. **HIV-Related Behavior.** Sexual-risk questions ask about type of sexual behavior lifetime and in past three months (i.e., anal, oral, vaginal), frequency of sexual intercourse, age of sexual debut, number of sexual partners and frequency of condom use, and condom use intentions in the next 3 months. These items are used to compute a **Sex Risk Score** (0 to 4), which reflects sexual behavior for all youth, as done in Project STAR. **Substance Use.** Questions ask about alcohol and marijuana use including frequency and quantity. **Cross-talk.** Two items concern discussion with peers about HIV attitudes and skills to assess for potential cross-talk between those in different interventions.(40)

HIV/Sexual Risk Cognitions and Attitudes. Our brief scales (developed and refined over the past 20 years) to measure HIV-related knowledge and attitudes in adolescent have demonstrated adequate test-retest reliability ($r = 0.67$ to 0.83) in a delayed education control group over three weeks and adequate internal consistency (alpha = 0.62 to 0.79).(85,86) The knowledge and attitudes scales have proven to be sensitive to educational impact. **HIV Knowledge.** A twenty-item (true, false, uncertain) scale surveys routes of transmission, casual contact misconceptions, general information and course of illness. It increased significantly with STAR compared to the control condition that provided similar HIV knowledge, presumably due to the decrease in cognitive errors from the STAR training. **Self-Efficacy for Condom Use Scale.** The scale contains 13 items that reflect the context of condom use, such as “could use a condom when I’m very upset” and was found to have a good factor structure and a strong alpha of 0.9.(87) Self-efficacy in emotionally stressful situations improved in STAR, presumably due to the improvement in affect management. **Affect Dysregulation Scale.** A six item scale assessing adolescents’ perceived abilities to manage emotional upset (e.g., “In the past three months, I have had trouble controlling my feelings.” The scale has a Cronbach’s alpha = .72. The scale correlates strongly with behavioral risk in a sample of youth in mental health treatment.(48)

Advantages of Condom Use Scale. (88) This scale has 13 items (alpha=.78) to assess cognitions of condom use (e.g. “it would be safer”), which are relevant to the interventions focus on cognitive monitoring.

Because of the prevalence of psychological symptoms and trauma history, this will be assessed to describe the sample. **Childhood Trauma Questionnaire (CTQ).** This is a 28-item youth self-report measure that assesses history of physical, sexual and emotional maltreatment. It yields a subscale score for each domain of maltreatment as well as a total score. The CTQ has demonstrated excellent psychometric properties in clinical and non-clinical samples ($\alpha = .92$).(89) **The Brief Symptom Inventory (BSI).** This measure yields symptom scales and global indices and has norms for adolescents. The reliability, validity, and utility of the BSI instrument have been tested in more than 400 research studies.(90)

Youth Risk Behavior Surveillance System (YRBSS). We will use items from the YRBSS (CDC, 2001) to assess adolescents’ tobacco use, dietary behaviors, and physical activity, and behaviors that contribute to

unintentional injuries. As with all other measures, the YRBSS will be administered to adolescents in all three conditions.

For descriptive purposes, data on feasibility and adherence will be collected. **Agency feasibility** is the ability to access and use the program successfully, assessed by the number of completed modules and the contacts with VBI and RIH regarding technical issues, clinical questions or clarification. **Participant treatment adherence** is the percentage of completed activities and sessions.

Data Analysis

Qualitative Data (Focus Group and Qualitative Interview). Focus group notes will be analyzed using the “Rapid Approach” of Kruger and Casey (2000) as described earlier to tabulate the common themes to each probe in order to refine the translation tables.(81) Matrix displays will be used to organize and analyze qualitative data gathered during the developmental individual interviews based on procedures described by Miles and Huberman (1994).(91) This approach allows for examining each individual’s responses in relation to each other (i.e., within case analyses) as well as comparing responses across interviews (i.e., between case analyses). A matrix format for entering and displaying data, which may include words, phrases, or direct quotes, with each of the primary topics having a separate matrix to identify common themes and concepts of importance. These analyses will guide revisions of the digital material. For example, commonly mentioned dysfunctional cognitions, if not already listed in STAR, will be added to increase the relevance of D*STAR. Qualitative data will help identify specific points of modification that will make activities more acceptable and impactful.

Phase 1 Quantitative Data (Open Trial). Validation Check: Mean scores of 24 on the CSQ and 30 on the SEF, comparable to “good,” will be deemed as acceptable for each complete session. Modifications to each of the activities and session will be based on these scores and the qualitative feedback. To judge the preliminary impact of the developed sessions HIV cognition and attitude scales will be examined from pre to post test using a one-tailed paired *t*-test with alpha = .05. **Power** is 0.8, with *n*= 26, to distinguish an effect size of 0.5, similar to the STAR study.

Protection of Human Subjects and Safety Monitoring Plan

Human Subjects Involvement, Characteristics and Design

The proposed research study is comprised of two phases. In the 24 months of **Phase 1**, we will develop and refine digital versions of 4 sessions of STAR: two sessions dealing with instruction in affect regulation in sexual situations and role-playing practice of those affect regulation skills, and two sessions of STAR dealing with instruction in cognitive monitoring in sexual situations and role-playing practice of those cognitive skills. This will be accomplished by an iterative process of digital development between the developers of STAR and our technology partner, Virtually Better, and with feedback from 60 adolescents in mental health treatment and community stakeholders. In the 36 months of **Phase 2**, we develop and refine digital versions the remaining sessions of STAR and a digital general health promotion (HP) intervention in an iterative process with Virtually Better, building upon the essential content areas and refinements developed in Phase I. Also, we will conduct a randomized control trial of D*STAR compared to the time matched digital HP intervention among 120 adolescents ages 13 to 20 in mental health treatment.

Inclusion Criteria. Adolescent males and females, ages 13 to 20 years, who are in mental health treatment will be eligible for enrollment in each phase of study according to the following criteria: 1) English speaking, 2) adolescent assent given to participate in the study, 3) consent of a parent/legal guardian and HIPAA research authorization permission and 4) attending an alternative / therapeutic school, mental health day treatment program, partial hospital program, or therapeutic group homes. There will not be overlap between subjects in the Development Phases, the Pilot Trial and the Randomized Controlled Trial.

Community stakeholders will be eligible for enrollment in the focus group phase of the study according to the following criteria: 1) staff members from a mental health setting, parents of an adolescent in mental health treatment, and staff members from relevant community organizations, such as those serving lesbian, gay, bisexual, transgender, and questioning youth (see letters of support from Bradley Hospital, Gateway Health, AIDS Care Ocean State and Youth Pride Rhode Island), 2) English speaking and 3) consent and HIPAA

research authorization permission. Exclusion criteria include: 1) not English speaking and 2) inability to provide consent.

Sources of Materials

Research Material Obtained from Living Human Subjects. Research material obtained from participants includes questionnaire data, and audio-tapes from qualitative interviews and focus groups. For development of the intervention, subjects will complete qualitative interviews and focus groups in-person regarding their reactions to the digital multimedia activities. The focus groups and qualitative interviews will be recorded and they will take place at the Bradley Hasbro Research Center. The audio-taped interview and written surveys of their reactions to the Intervention will be the sources of material for this phase. For both the Pilot and Randomized Controlled Trials, participants will complete computerized questionnaires about their demographic information, sexual behavior, substance use, affect regulation, and HIV related knowledge/attitudes. Questionnaires will be given at a Lifespan facility or cooperative agencies, and they will be completed at entry to the study, after the last intervention session and 3 months later. Any data collected outside of Lifespan will be transported on a laptop back to Bradley Hasbro Research Center where it will be backed-up and deleted immediately.

Linkages to Subjects and Access to Subject Identities. For each stage of the research, participant names and contact information will be maintained in a recruitment/enrollment database during the course of the study. Once individuals enroll in the study, names will be linked to participant ID number in this database, which will be kept in a restricted access folder on a secure server. All name/ID number files will be assigned a code name unrelated to the name of the study. Signed consent and assent forms will also be kept in a locked file cabinet, separate from any other project data. Once data collection is completed, the corresponding recruitment/enrollment database will be deleted as it is unnecessary to maintain the link between participant identity and study data. Destruction of the Master Clinic Patient Lists must be witnessed and documented on the Master List Verification of Destruction document, which will be maintained in the site's regulatory files. Furthermore, any information collected as part of this study will be accessible only to research staff that has completed mandatory training in the protection of human subjects.

Potential Risks

Every effort will be made to ensure that study participants are protected from risks. The risks are as follows: 1) potential coercion, 2) loss of confidentiality, 3) emotional discomfort during the assessment and/or program sessions. The protection against each risk is described in detail below under Adequacy of Protection Against Risk.

Adequacy of Protection Against Risk

Recruitment and Informed Consent. The risk of potential coercion will be minimized by following standard procedures for obtaining the informed consent from participants, parents, and assent from teens. Recruitment for all phases of the project will involve the same screening procedures. Adolescents will be recruited from mental health related day programs (alternative / therapeutic school, mental health day treatment program, partial hospital program, outpatient clinic, or therapeutic group home) in southern New England. Programs will identify youth in the eligible age range and obtain consent to contact permission from parents / guardians (see consent to contact form). The consent to contact form describes D*STAR, including who will participate in the study and what is expected of research participants, and it explains that participation is voluntary and that all of the information participants provide will be kept confidential. The form also asks parents / guardians (including biological parents, stepparents, legal guardians, or, in the case of wards of the state, the regional supervisor of the Department of Children, Youth and Families (DCYF)) to sign their agreement or disagreement with being contacted. If interested, research staff will contact the parents / guardians to determine initial eligibility and then screen the adolescent for eligibility over the phone. Study personnel will fully explain the study procedures, risks, benefits, and alternatives to participants. Participants and their parents will also be reminded that study participation is voluntary and that refusing to participate or withdrawing from the study at any time will not result in any negative consequences. Research staff will make

every attempt to obtain parental consent in person, however if this cannot be achieved phone calls will be made to the parents / guardians to ensure they understand what the study entails (see below). In all cases above, participants will be assured that they are free to withdraw from the study at any time and that if they do withdraw any data collected up to that point will be destroyed/stripped from any data files (see Protection Against Risk for data handling procedures). As noted above, participation in all stages of the intervention is entirely voluntary and subjects are free to withdraw from the project at any time. Discontinuation or decision not to participate will not jeopardize routine care in their mental health program in any way.

Consent of community stakeholders: At a routine meeting of community stakeholders, an announcement will be made stating that an opportunity exists for members to participate in a research study in which they will be reviewing and providing feedback on a multimedia-based HIV prevention and safe sex education that has been developed for adolescents. Those interested in participating will be contacted at a later date and will meet individually with a researcher to discuss consenting. Participants will be informed that their participation in the study is voluntary and will not effect their current position and/or child's treatment.

Obtaining Informed Consent in Special Cases. Consent/assent of an adolescent (<18) from a mental health treatment program without a parent or guardian present: Families will be sent a consent to contact form (see above). If parents / guardians are interested and have signed the consent to contact form research staff will call them over the phone to screen the adolescent for eligibility. Families will be fully informed in the consent form and, either in person or by phone, about the purposes and procedures of the study. Participants and their parents will also be reminded that study participation is voluntary and that refusing to participate or withdrawing from the study at any time will not result in any negative consequences. If the parent / guardian cannot be consented in-person we will send them a consent form to sign, and we will verify their written consent, discuss the details of the study, and their child's participation over the phone. The consent form will be signed by the guardian before the adolescent will be allowed to participate in the study. Adolescents whose parents / guardians have signed the consent will be told of the consent and study procedures, and expectations will be explained in a private setting. Adolescents will be reminded that participation is voluntary and will not effect their mental health treatment. Only those adolescents who provide assent will be enrolled. All adolescents who have signed consent forms indicating parental permission to participate in the study, and have signed assent, will be eligible for the study.

Protections Against Risk

Breach of Confidentiality. Potential risk will be minimized by strictly adhering to the guidelines for research outlined by the Lifespan IRB, Rhode Island state law, the Federal Health Insurance Portability and Accountability Act of 1996 and its regulations ("HIPAA"), and the DHHS Federal Policy for the Protection of Human Subjects (45 CFR Part 46 Subpart D). This will include identifying participant research data by numeric ID only and maintaining any records containing potentially-identifying information separate from any research data. All research data (written records and audiotapes of program sessions) will be kept in a locked file and electronic data will be password-protected. All of these study-related materials will only be accessible to research staff. No names, only identification codes, will be used in presenting data in lectures, seminars, and papers. Information will be released only with written consent of the parent/guardian.

By enrolling in the study, other individuals may know that a participant is in mental health treatment. This may result in a breach of confidentiality. This can be addressed by research staff. During the consenting process it will be explained to participants that all of those in the research study are in mental health treatment and will be known to them. To further protect against the breach of confidentiality by other research participants, research staff will explain and stress the importance of confidentiality prior to each session, just as it was explained during the consenting process. Prior to each session of group activities research staff will review the group expectations as they pertain to respect for individuals and their privacy. These expectations and guidelines will establish that although research staff will make every effort to minimize risk for breach of confidentiality, research staff cannot control the actions of other group members outside of the research activity setting. Facilitators will be trained in group management. Additionally, a school staff member will be present at all group sessions to monitor behavior and to ensure compliance with school rules.

Participant confidentiality will be breached only to protect the safety and welfare of research participants and only in accordance with state and federal law. If child abuse or neglect is reported, a report

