Hypothesis: In a pre-posttest design, participants will show improvements in relevant HIV cognitions and attitudes.

Phase 2: Specific Aims

1. To develop and refine digital versions the remaining sessions of STAR and a digital general health promotion (HP) intervention, building upon the essential content areas and refinements developed in Phase I.

2. To conduct qualitative evaluations of the feasibility, utility, and acceptability of D*STAR and the digital HP intervention with adolescents in mental health treatment, and community stakeholders, which may include parents of youth in mental health treatment, staff from mental health facilities, and staff from relevant community organizations serving youth. Hypothesis: Both digital interventions (HP and D*STAR) will be rated by youth and community stakeholders as enjoyable, useful and easy to implement.

3. To conduct a randomized control trial of D*STAR compared to the time matched digital HP intervention among 120 adolescents ages 13 to 20 in mental health treatment.

Hypothesis: Participants in D*STAR will report safer sexual behaviors, greater HIV knowledge and greater self-efficacy for HIV prevention skills than participants in digital HP at three months follow-up.

A. SIGNIFICANCE

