Each storyboard activity will be created in a digital format and will be informed by the iterative focus group feedback described above. VBI will ensure that the prototypes are technically feasible and make maximal use of multimedia capabilities. RIH will ensure that the prototypes are consistent with the content and process elements of STAR and that they are appropriate for adolescents. Feedback on the Stage C digital material will be obtained from approximately 15 youth in mental health treatment. Two, 90-minute qualitative interview sessions with adolescents will occur in our research lab and will be used at this stage to gather detailed critiques. The sample of adolescents in mental health treatment will adequately represent the demographic characteristics (age, gender, race, ethnicity, gender orientation) of the target population. Each activity will be reviewed and critiqued as to its acceptability by adolescents and its likelihood of conveying the intended material. Interviews will probe for ambiguous material and comprehension of content. In addition, each participant will rate each D*STAR activity as to its clarity, relevance and appeal (see draft rating forms in Appendix). Interviews will continue until no new information is obtained (estimated to be 10-15 youth). Digital material will again be refined by VBI and RIH based on feedback from the adolescent interviews and from the community stakeholders and compiled into complete sessions. Participants will also complete the Session Evaluation Form (SEF) and the Client Satisfaction Questionnaire (CSQ) (see Measures) to assess the clarity, relevance and appeal of the activities and their over-all reactions to the sessions.(82,83) **Validation check:** Mean scores of 24 on the CSQ and 30 on the SEF, comparable to “good,” will be deemed as **acceptable** for each complete session. The process of refinement will continue with more youth, if needed, until all four sessions meet these criteria

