Phase I, Stage D: Open Pilot Trial (Months 17-24). The validated D*STAR sessions will be tested with a new cohort of approximately 30 youth in mental health treatment. Subjects will participate in four weekly, one-hour sessions, and after each session will complete a brief (five-minute) questionnaire about the acceptability and relevance of the session. Assessments and the sessions may occur in the participants' school, place of mental health treatment or in our office. To determine the preliminary impact of the sessions, youth will complete several measures of HIV cognitions and attitudes (see Measures). Participants will be asked to complete one 60-minute computerized questionnaire before the program starts, and one computerized questionnaire one month after the program. The sample will have power 0.8 to discern a moderate effect size on attitudes in a pre-posttest design (see Data Analysis). The process of refinement will continue with more cohorts, if needed, until change in attitudes is observed.

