All eligible and consented/assented adolescents will complete a demographics form (age, gender, race, ethnicity, parent education, and household income). During Phase 1 all measures will be delivered via paper and pencil. In the Phase 1 Open Trial acceptability and relevance of the sessions will be answered in paper and pencil format, but all other measures will be administered via audio computer assisted self-interview (ACASI) to increase adolescent comfort reporting on sexual and substance use attitudes and behaviors. The ACASI will be administered prior to the start of the intervention, immediately after the intervention, and then 1 month later. In the Pilot and RCT stages of Phase 2, all measures will be administered via computer assisted self-interview (CASI) to increase adolescent comfort reporting on sexual and substance use attitudes and behaviors. The CASI will be administered prior to randomization, immediately after completing the final intervention session, and then 1 month later for the Pilot stage or 3 months later at the RCT stage.

Phase 1: Focus group assessment and Individual Interviews (see guides in the Appendix)

Session Evaluation Form (SEF). The SEF is a brief 13-item questionnaire that will be given to intervention participants at the end of each session. This questionnaire consists of 10 items on a 4-point response scale aimed at eliciting information about the participant's experience with the session (i.e., was the session interesting, was it relevant to their life, did they learn from the session). Three open-ended items query participants about what was most and least useful about the session.(82)

Client Satisfaction Questionnaire–8 (CSQ-8). The CSQ-8 will be used at the completion of the intervention to assess the participant's satisfaction with the intervention, including the procedures, quality and quantity of service, outcome, and general satisfaction. These domains are assessed on a 4-point response scale with individually specified anchors. In addition, three open-ended questions are included that solicit comments about what respondents liked most and least about the intervention. The CSQ-8 has demonstrated high internal consistency across a large number of studies with alpha coefficients ranging from .83 to .93.(83)

Phase 1 Open Trial Measures

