During any phase of the study, if research staff determines that a participant is an acute medical or psychiatric risk, the PI or licensed designee will meet with the participant individually for further assessment and notify the participants’ parents of any clinical needs. Staff at the mental health program will also be notified, if indicated. Acute risks would include severe medical illness, or the development of any other severe psychiatric symptoms or disclosure of sexual or physical abuse. Any subjects who exhibit acute risks will be evaluated immediately by emergency room clinical staff at Rhode Island Hospital, or if less acute, by an independent clinician that day. Less severe medical needs or distress can be managed by staff or PI over the phone or with an individual interview. The PI and/or staff will meet with participants and/or families to review concerns and to make referrals for continuing care as needed. Of note, members of the proposed research team have substantial prior clinical (medical and psychiatric) and research experience in care of youth in mental health treatment as evidenced through their biographical sketches.

Potential Benefits of the Proposed Research to the Subjects and Others

Importance of Knowledge to be Gained. We hope that our intervention will be successful in addressing the unique HIV prevention needs of youth in mental health treatment and think that the clear examination of these questions outweighs the previously mentioned risks. The effectiveness of a novel, scalable, technology driven, HIV prevention intervention is understudied with this population. Given that adolescents in mental health treatment are at greater risk for HIV and other STIs than their peers, and the paucity of easily available intervention programs for this population, the knowledge to be gained from this research is significant. The risks to participants are minimal in relation to the importance of the knowledge to be gained.

Reimbursement for Time and Effort. In Phase I participants will be reimbursed \$50 for their participation in the focus group. Qualitative interview participants will be reimbursed 50 for each individual interview, so will receive \$100 if they complete the two sessions. Participants will be reimbursed \$50 for baseline and postintervention assessments during the Phase 1 Open Trial, so will receive \$100 if they complete both assessments. Subjects in all stages will be compensated \$15 for local travel to assessments.

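### The Phase 1 open trial has only a positive written exit, and the stated one-tailed .05 and power 0.8 describe one scale in one cohort, not this rule

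*Combined protocol and SAP*

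**What the plan says.** Phase I, Stage D (Open Pilot Trial, months 17-24) tests four digital sessions in a new cohort of about 30 youth, to gauge their preliminary impact on several measures of HIV cognitions and attitudes. On power it says: "The sample will have power 0.8 to discern a moderate effect size on attitudes in a pre-posttest design", and refers to Data Analysis. The next sentence is the continuation rule: "The process of refinement will continue with more cohorts, if needed, until change in attitudes is observed".

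Data Analysis, under Phase 1 Quantitative Data (Open Trial), says: "HIV cognition and attitude scales will be examined from pre to post test using a one-tailed paired" t-test at alpha .05, with power 0.8 at n = 26 for an effect size of 0.5. The hypothesis in the Specific Aims is also plural and names no scale: "In a pre-posttest design, participants will show improvements in relevant HIV cognitions and attitudes".

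The earlier refinement loop, in Stage C, has a numeric threshold for each session: "Mean scores of 24 on the CSQ and 30 on the SEF".

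The plan is not consistent on when the post-test takes place. Stage D has one questionnaire before the program and "one computerized questionnaire one month after the program". Measures says: "The ACASI will be administered prior to the start of the intervention, immediately after the intervention, and then 1 month later". Reimbursement for Time and Effort pays for "baseline and postintervention assessments during the Phase 1 Open Trial" and totals $100 at $50 each, which implies two assessments in all.

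**The concern.** A stage that judges impact needs a way to conclude that impact was not shown. Here a cohort without change leads to refinement and another cohort, and the only written ending is a cohort with change. The plan does not say which scale decides, whether one scale or all must change, how many cohorts may be run, or how the stage is reported if no cohort shows change.

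What is at stake is the meaning of a statement that the open trial showed preliminary impact. The reader will attach the plan's .05 and 0.8 to that statement, but those figures belong to a single test in a single cohort.

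**Working it through.** **Inputs.** From Data Analysis: one-tailed paired t-test, alpha .05, n = 26, standardised effect 0.5. From Stage D: about 30 youth per cohort, months 17-24. From Measures: up to four candidate scales (HIV Knowledge, Self-Efficacy for Condom Use, Affect Dysregulation, Advantages of Condom Use). Assumed, because the plan is silent: change means one-sided p < .05, cohorts are analysed separately with 26 completers each, and the scales' change scores correlate 0.3.

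**1. The plan's own figure.** Power = P(T > t(.95; 25)), where T is noncentral t with 25 degrees of freedom and noncentrality 0.5 × √26 = 2.550. The critical value is 1.708, so power = 0.798. The stated 0.8 reproduces for one scale in one cohort.

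**2. One named scale, no true change.** With k separate cohorts the chance of at least one pass is 1 − 0.95^k.
- One cohort: 5.0%.
- Two cohorts: 1 − 0.95² = 9.75%.
- Three cohorts: 1 − 0.95³ = 14.3%.

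**3. Any scale suffices, no true change.** Let p be the chance that at least one scale passes in one cohort (simulated, 200,000 runs, n = 26). Two separate cohorts give 1 − (1 − p)².

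| Scales | Correlation | One cohort | Two cohorts |
|---|---|---|---|
| 3 | 0 | 14% | 26% |
| 3 | 0.3 | 13% | 24% |
| 3 | 0.5 | 12% | 22% |
| 4 | 0 | 19% | 34% |
| 4 | 0.3 | 16% | 30% |
| 4 | 0.5 | 14% | 27% |

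Three scales is the count if HIV Knowledge is not treated as an attitude; four is the count if it is.

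**4. All scales must pass.** With four scales at correlation 0.3 the false-pass chance in one cohort is about 0.05%. Power, with a true effect of 0.5 on every scale, then falls to about 0.49. This reading loses the stated 0.8 instead of the stated .05.

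**5. How many cohorts could fit.** Four weekly sessions plus a one-month assessment take about two months. Months 17-24 are eight months, so three or four consecutive cohorts could fit at most, before allowing for recruitment and revision. The 60 Phase 1 adolescents in the Human Subjects section match 15 + 15 + 30, that is, one open-trial cohort.

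The .05 and the 0.8 therefore hold together only for one named scale in one cohort.

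**The case against.** The strongest reply is that this is iterative development. Sessions are revised between cohorts, so each cohort tests a different version, and a final version tested once in a new cohort on a scale named beforehand keeps its own .05. That stands. It is also why the figures above treat cohorts separately; pooling would mix versions, and the plan does not propose it. It does not rescue the stage-level claim, because the plan names no scale and lets the stage run until a cohort passes.

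Three stronger readings are tempting, and the documents do not support them.
- A reader might infer that the plan has no criterion at all. Data Analysis gives a test, a direction and an alpha for judging preliminary impact. What is missing is its link to the continuation rule.
- A reader might infer that the stage can never produce a negative finding, or that the loop will run without end. A cohort without change is a negative finding, and its stated consequence is refinement. The months 17-24 window and the planned 30 youth make a long loop unlikely. Neither is written as a stopping limit, though, and neither says how the stage is reported if it ends without change.
- A reader might infer that the RCT is compromised. The RCT Stage and the Inclusion Criteria both exclude overlap with earlier participants, so the randomized comparison keeps its error rate.

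It is also fair to say that the multi-scale figures depend on assumed counts and correlations. They show what the ambiguity allows, not a measured error rate.

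**Conclusion.** The point holds as a minor one. The continuation rule has a positive exit only, and the stated .05 and 0.8 do not describe the claim that the stage would support. For one scale the false-pass chance is 5.0% with one cohort and 9.75% with two. If any of three to four scales counts, it is about 13-16% and 24-30%. These figures assume that change means one-sided p < .05, that cohorts are tested separately at n = 26, and, for several scales, a correlation of 0.3.

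The consequence is limited to a preliminary claim from an uncontrolled pre-post stage, where change would not prove a program effect in any case. The post-test discrepancy is real but separate: it enters none of these figures, and it leaves open which post-test decides.

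**What to change.** Replace the continuation sentence in Stage D with text such as:

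> Preliminary impact will be judged on [one scale named by the sponsor] at [one post-test], using the test in Data Analysis. Refinement and retesting in new cohorts may continue only within months 17-24, up to [a stated number of] cohorts, each analysed separately. If the last cohort shows no change, the open trial will be reported as not showing preliminary impact. All cohorts and scales will be reported with confidence intervals; scales other than the named one are descriptive.

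In Stage D and Data Analysis, state that .05 and 0.8 apply per cohort to the named scale, and give the overall error for the chosen number of cohorts (9.75% for two at .05).

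Splitting alpha is optional. Two cohorts at .025 each give 1 − 0.975² = 4.9% overall, but power per cohort at n = 26 falls from 0.80 to 0.69. The chance of detecting the effect within two cohorts is 1 − (1 − 0.688)² = 0.90, if the effect is 0.5 in each. A missed effect here leads to needless redevelopment, so keeping .05 and disclosing 9.75% is also defensible.

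If more than one cohort is allowed, make the 60 adolescents in the Human Subjects section consistent with that number; a second cohort of 30 would make it about 90. Separately, reconcile the post-test times in Stage D, Measures and Reimbursement.

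The cost is a short amendment, which the plan routes through the IRB, and possibly a larger planned enrolment. The scientific downside is that, under a fixed limit, a late version of the sessions may not be retested in Phase 1. If the stage has already been run, which the documents do not say, reporting every cohort and every scale with confidence intervals is still possible.
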